### Standard of Care vs. Research Procedures

#### Standard of care:

All outcome measures are standard of care procedures that are collected at the doctor's office. These procedures are not provided specifically for this research study.

- o CT scan to assess fusion status at 1 year post-op
- o Cellular analysis of the bone marrow aspirate quality
- o and health-related quality of life measures previously defined
- o Blood loss
- Length of stay
- o Radiological outcomes
- Complications
- o Narcotic usage

### **Research Procedures:**

- Occilection of Bone marrow aspirate is standard of care but using the Smart Prep Bone Marrow Concentrate system, combining the BMAC with the cancellous bone chips with the Graft Delivery Pack, and dosing as outlined in the Procedures section are unique to the research procedures.
- o *Randomization Process:* The process of randomization will be computerized and completed by an individual not associated with the study. The randomization will be performed at 1:1:1 ratio between the three arms. Sequenced and sealed envelopes or a similar randomization technology approach will be used.

### Blinding: Patient, Reviewer and Physician

- The patient will not be blinded to his/her treatment assignment.
- The reviewer of the clinical outcomes as well as the radiographic analysis post-operatively will be blinded to the surgery that the patients receive.
- The surgeon performing the surgery will not be blinded.

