### Intervention

Patients will receive a lumbar fusion with one of the three interbody support grafts listed below:

• INFUSE rhBMP-2 Bone Graft used according to its approved FDA labels, both the original approval performed from an anterior approach using titanium cages as well as the more recent approvals with the use of PEEK cages from a posterior interbody approach. BMP will be placed in a PEEK cage and to be inserted in a posterior or anterior approach;

or

• Allograft infused with adult stem cells from the bone marrow aspirate concentrate harvested from the iliac crest. Harvest® BMAC System delivers high stem cell concentration to the graft site and will be used according to its approved FDA label.

or

- Autograft with bone marrow aspirate (control)
- Enrollment will be 1:1:1
- The study will determine and compare differences in fusion rate and health related quality of life parameters at 6 weeks, 3 months, 6 months, 1 year, and 2 years postoperatively.
- Pre-operative standard care measures include narcotics usage and health-related quality of life measures: Oswestry Disability Index (ODI), Visual Analog Scale (VAS), Euro-Qol 5-dimension (EQ-5D), Health State Scale, PCS, PROMIS Surveys outlined below:
- PROMIS Bank V11 Pain Interference (Adaptive)
- PROMIS Scale v1.0 Pain Intensity 3a(Auto-scoring)
- PROMIS Bank v1.2 Physical Function(Adaptive)
- PROMIS Bank v2.0 Mobility(Adaptive)PROMIS Bank v2.0 Upper Extremity
  \* While PROMIS will be collected, it will be optional in this study due to limitation of getting patients to collect PROMIS at enrolling surgeon's site. Data will be collected from pre-operative standard-care measures for this study
- Intra-operative standard care measures include intra-operative and peri-operative blood loss, length of stay in hospital, bone marrow quality, and complications. Data will be collected from intra-operative and peri-operative standard care measures for this study.
- Post-operative standard care measures include fusion status at 1 year via CT scan, and health-related quality of life measures previously defined via RedCAP, radiological outcomes, and complications. Data will be collected from post-operative standard care measures for this study
- The radiologist will be blinded to the patient's treatment at the time of postoperative outcomes analysis. The patients will not be blinded to their assigned treatment arm.

PI: [name]

- Outcome measures will include:

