  - 1. Pre-operative measures: narcotic usage, and health-related quality of life measures previously definedIntra-operative measures: intra-operative and perioperative blood loss, length of stay, complications
  - 2. Post-operative measures: fusion status at 1 year via CT scan, and health-related quality of life measures previously defined, length of stay, radiological outcomes, complications
- The patient and reviewer [of the clinical outcomes as well as the radiographic analysis postoperatively] will be blinded to the patient's treatment.

All materials procured from Harvest® BMAC System is FDA approved:

- Collection of Bone Marrow Aspirate Concentration (autologous adult stem cells) for Fusion
  - Bone Marrow Aspirate (BMA) will be aspirated from the anterior iliac crests using an 11 gauge 5 side-hole Jamshidi needle and a 60 mL syringe flushed with heparinized saline. Following a midline incision, the needle will be directed at about 30° to the vertical and parallel to the plane of the crest and inserted to a depth of approximately 5 to 8 cm (Figure 1). 1 mL will be sent for cellular analysis.

Figure 1

- Sixty mL of BMA will be aspirated while rotating and slowly withdrawing the needle toward the cortex. This step will be repeated on the contralateral ileum for a total of **60**, **120**, **or 180** mL of BMA. The BMA is then pooled into a blood bag containing Anticoagulant Citrate Dextrose Solution (ACD-A).
- The BMA will then be placed into the SmartPrep® Bone Marrow Concentrate (BMACTM, Harvest Technologies Corp., Plymouth, MA) system and concentrated in 15 minutes to a final volume of **10**, **20**, **or 30 mL**.
- The BMAC will then be combined with packed allograft cancellous bone chips using the Graft Delivery Pack (GDP, Harvest Technologies Corp.) yielding two or three 10 mL surgeon constructed bone logs (Figure 2). The allograft bone will be obtained routinely from the bone bank in the operating suite.

PI: [name]

Figure 2

• The allograft logs will be placed in the lateral gutter and interbody cages.

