#### rhBMP-2 Fusion

- Two mL of BMA will be aspirated in identical procedure to the BMAC group for comparison of aspirate quality.
- For patients selected to receive BMP, 12 mL BMP will be applied at the surgical site of the interbody fusion using a collagen sponge following manufacturer's directions.
- BMP kit use per level:
  - o 1 Level Fusion: Extra small kit (1.4 cc)
  - o 2 Level Fusion: Small Kit (2.8cc)
  - o 3 Level Fusion: (4.2 cc)
  - o 4 Level Fusion: Medium Kit (5.6cc)
  - o 5 Level Fusion: (7.0 cc)

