#### **Control Fusion**

• As per standard of care, the control group will receive 15cc – 45 cc of allograft with autograft and bone marrow aspirate at each level. The iliac crest is the common donor site

PI: [name]

for autograft. Bone marrow aspirate will also be processed for data collection. Both will be harvested and combined in routine fashion to make the bone graft.

• Using the standard technique for anterior lateral fusion, the bone graft will be laid onto the desired site of fusion.

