# Aim 1: Clinical Study

This study will analyze the clinical and radiographic outcomes in terms of pre-operative measures, intra-operative measures, and post-operative measures followed-up for in the three groups.

Primary Outcome Endpoint: As per the primary outcome measure, fusion status at 1 year will be assessed via CT scan by an independent radiologist. Clinical outcomes will be defined by patient reported and health-related quality of life measures previously defined. Differences from preoperative visit to post-operative time points will be compared between the 3 groups by Student t-tests. Based on preliminary data, improvements are expected in these outcome measures: ODI from 33.42 (SD:6.22) to 26.75 (SD:8.19); SF-12 PCS from 29.00 (SD:6.05) to 31.42 (SD:6.05); SF-12 MCS from 31.42 (SD: 6.50) to 35.75 (SD: 13.82); NRS from 8.17 (SD: 1.27) to 5.93 (SD: 1.90). Multivariate regression analysis, controlling for age, sex, race, and charlson comorbidity index, will be performed to determine the effect of treatment on reaching MCID values, as defined in Parker et al 2012.[2]

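### Masking of the CT reader rests only on withholding the assignment; donor-site and gutter-graft differences may reveal the arm on some scans, and no image-handling safeguard is described

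*Combined protocol and SAP*

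**What the plan says.** The primary outcome is set under Aim 1: Clinical Study: "fusion status at 1 year will be assessed via CT scan by an independent radiologist". Two sections promise masking of that read. Under Intervention: "The radiologist will be blinded to the patient's treatment at the time of postoperative outcomes analysis". Under Blinding: Patient, Reviewer and Physician, the promise extends to the operation itself: the reviewer of the "radiographic analysis post-operatively will be blinded to the surgery that the patients receive". The roles listed under Data Monitoring also give the independent reviewer and the data analyst no knowledge of group assignment. The patient and the surgeon are unblinded according to the Blinding section.

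The three procedures are described as follows.

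- **Control** (Control Fusion): allograft with autograft and marrow aspirate at each level. On the source of the autograft: "The iliac crest is the common donor site".
- **BMAC** (Intervention): marrow "will be aspirated from the anterior iliac crests using an 11 gauge 5 side-hole Jamshidi needle". On placement: "The allograft logs will be placed in the lateral gutter and interbody cages".
- **BMP** (Intervention and rhBMP-2 Fusion): "BMP will be placed in a PEEK cage and to be inserted in a posterior or anterior approach". It is "applied at the surgical site of the interbody fusion using a collagen sponge following manufacturer's directions". A 2 mL aspirate is taken by the same technique as in the BMAC arm.

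The 1-year CT is listed as standard of care. No section describes cropping or coding of the images, or a check on whether the masking worked.

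**The concern.** Withholding the allocation list masks a reader only if the image does not carry the same information. Here the reader is said to be blind to the surgery, yet has to look at the operated spine, and the protocol's own procedures differ in ways that could appear there. Some fusion calls are likely to be borderline. A reader who recognises the graft may settle such scans differently in one arm, without intending to.

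The CT read is the endpoint that masking could best protect, because the questionnaires are completed by patients who know their treatment. The arms are small, so a few influenced reads would be noticeable, and the plan has no means of detecting them.

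**Working it through.** The plan states no figure on this point, so there is none to reproduce. The check has two parts.

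**1. Which features could identify an arm, taking the text as written?**

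| Feature | Control | BMAC | BMP | Separates arms? |
|---|---|---|---|---|
| Iliac crest | Bone harvest, common but not mandatory | Needle aspiration | Needle aspiration, same technique | Could mark control; cannot separate BMAC from BMP |
| Lateral-gutter allograft | Position given only loosely, as the site of fusion | Stated | Not described | Could separate BMAC from BMP; not clearly BMAC from control |
| Cage | Not mentioned | Interbody cages, material not given | PEEK cage; titanium named in the label text | No |
| Surgical approach | Varies | Varies | Varies | No (Randomization Process) |

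Two cues remain: crest harvest and gutter graft. Withholding the assignment removes neither. Whether the reader sees them depends on facts the documents do not give: the CT field of view, and whether a donor defect is still visible at 1 year. Both are assumptions here.

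**2. How much does one read weigh?**

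Inputs: 20 enrolled and at least 17 expected to complete per arm (Sample Size Analysis); a 10% reduction in fusion against control as a reason to stop (Criteria for Action).

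Shift in an arm's fusion rate from k changed reads = 100 × k / n percentage points.

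- k = 1: 100/20 = 5.0 points; 100/17 = 5.9 points.
- k = 2: 200/20 = 10.0 points; 200/17 = 11.8 points.

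Two changed reads in one arm therefore produce a difference that meets the stopping criterion, if it is read as percentage points.

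Statistical significance needs more. Take a comparator arm with 19/20 or 16/17 fused, and an otherwise identical arm that loses k reads. Fisher's exact two-sided p first falls below 0.05 at k = 6 (p = 0.044 at n = 20; 0.039 at n = 17). At k = 5 it is 0.091 and 0.085.

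**Sensitivity, on assumed values only.** Suppose true fusion is 90% in both BMAC and control. Let X and Y be independent binomial counts of scans read as fused in control and BMAC. The quantity is P((X − Y)/n ≥ 0.10).

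| Assumed reading | n = 17 | n = 20 |
|---|---|---|
| Unbiased | 0.188 | 0.208 |
| BMAC read 5 points lower | 0.362 | 0.401 |
| BMAC read 10 points lower | 0.536 | 0.587 |
| Control read 5 points lower | 0.106 | 0.111 |
| Control read 10 points lower | 0.057 | 0.056 |

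The 5- and 10-point shifts do not come from the documents. The table shows how sensitive the comparison is in either direction and predicts no bias.

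**The case against.** The strongest reply is that the protocol does provide masking: the reader and the analyst are denied the assignment, and a surgeon and radiologist separate from the treating team are to do the radiographic analysis (Investigation schedule and follow-up). Incomplete concealment of visible surgical differences is a familiar limit of surgical trials. This stands, and it means the plan does not contradict itself here.

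A reader might go further and infer that every arm leaves its own signature on the CT, so that the primary read is not masked at all. The documents do not support that. BMAC and BMP patients have the same type of aspiration. The crest is only the usual donor site in control. Control graft could also lie in the gutters as far as the text says. Cages are named for both BMAC and BMP, and differing approaches add variation unrelated to arm. Visibility of the crest and of a healed defect is imaging knowledge, not protocol content.

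It would also be wrong to treat the CT read as the only masked outcome, since the Blinding section covers the reviewer of clinical outcomes too.

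Finally, nothing suggests that a reader would favour one arm. The 10-point difference arises about 19% to 21% of the time even with unbiased reading under the 90% assumption, so much of that instability comes from the sample size. Under the same assumptions a significant Fisher test remains uncommon: about 2% to 3% with a 5-point shift and 5% to 7% with a 10-point shift.

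What survives is narrower. Two plausible cues exist, and no safeguard against them is described.

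**Conclusion.** The concern holds in limited form. Masking of the primary CT read is asserted and rests only on withholding the assignment. Iliac crest harvest and lateral-gutter allograft may let the reader infer the arm on some scans, provided the crest and defect are visible on the 1-year CT. The documents do not show that the arm is recognisable on every scan or that masking fails.

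One influenced read is worth 5.0 to 5.9 points of fusion rate, and two are worth 10.0 to 11.8 points, which reaches the 10% fusion criterion if that is in percentage points. The size and direction of any actual bias cannot be determined from the documents. The case for acting is that the improvement to the primary read is cheap, not that a bias has been demonstrated.

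**What to change.** In Intervention and in Blinding: Patient, Reviewer and Physician, add that the reader scores fusion from a coded export of the 1-year CT cropped to the operated levels. Existing study staff prepare the export and remove the iliac crests, the scout image, the request text and any implant or operative notes.

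Optionally, the reader records a guess of the arm after scoring each scan, reported descriptively beside the primary result; chance agreement is one third with three equal arms. The guess measures unmasking and does not prevent it.

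The cost is a few minutes per scan, plus one field on the reading form if the guess is used. No extra scan, reader or patient is needed, and no treatment changes. Gutter bone stays visible wherever it lies within the operated levels, so masking is improved but not complete.

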# **Data Storage and Confidentiality**

Case report forms and all other documentation collected by the investigators and research coordinator will not contain subject names. Each subject will be assigned a subject code. The subject code will consist of 6 characters in an alphanumeric combination (for example nyu-001). The site will maintain the link between the subject code and the names. Primary data collection

PI: [name]

will be based on source-documented hospital chart reviews, notes on the source worksheets and subject interviews will be performed by study researchers or investigators at each clinical site. Data will be stored in individual subject binders and locked in a secure office and uploaded onto REDCap for electronic data capture. Only approved research coordinators/investigators will have access to the data.

# **Investigators Qualifications and Experience**

All patients are recruited through the NYU affiliated private office of [name] at the New York Spine Institute in Long Island, New York. Patients are consented by the investigator, study coordinators and persons completing research fellowships in orthopaedic surgery working exclusively on clinical orthopaedic research projects. These researchers all have experience seeing and consenting patients. These patients will be consented if they meet inclusion criteria. Independent reviewer will be a member of the NYULMC house staff and member of orthopaedic department. Reviewer will be a MD and be experienced in reading and interpreting radiograph outcomes.

# Subject Identification, Recruitment and Consent

As part of the standard of care, the subject will have an initial consultation with the PI/MD which includes appropriate physical and radiographic examinations. The subject will be informed of the nature of their spinal disease and treatment options, operative and conservation non operative care. Should the surgeon feel that operative treatment is the best option, they will be eligible for enrollment into this study. Their treatment will not be influenced by the existence of this study.

All study participants will be patients of [name]. The same care will be provided independent of the patient's willingness to be a part of the study. The 60 subjects to be accrued are based on investigator's caseloads. Only patients who are able to understand the English language will be allowed to participate in the study due to the nature of the validated questionnaires that will be given to them.

PI will identify his clinic patient's eligibility for enrollment into the study using inclusion/exclusion criteria. Should the PI/surgeon feel that operative treatment is the best option, subject will be eligible for enrollment into this study. Their treatment will not be influenced by the existence of this study. PI anticipates to enroll up to 4 patients per month, allowing for completion of enrollment in 15 months, but no longer than 2 years.

# **Process of Consent: Subject Capacity & Subject Comprehension**

Potential participants will be asked to review a copy of the informed consent form prior to enrollment. The investigators will use an informed consent form that has been approved by the Institutional Review Board (IRB) at this institution. Patients will be recruited when meeting all inclusion and exclusion criteria. Once recruited, all subjects will go through the informed consent process. One or more of the research team members will explain, in simple terms, the details about the outcome collection and the subject's involvement.

Patients must have the capacity to comprehend and give informed consent. Patient will be given the opportunity to ask questions prior to signing the informed consent (ICF). Comprehension of

PI: [name]

the study will be tested by asking the subject and his/her family follow-up questions about their understanding of the study procedures and follow-up process after informed consent has been given. During this time frame and throughout the time period of the study, the research team will re-educate the patient on the study. Additionally, this will provide the patients with the opportunity to make a fully informed decision about their participation in the outcomes data collection, prior to signing the ICF. This will ensure that all subjects understand the nature of the outcomes data collection, the risks and benefits involved, and their commitment to complete all follow-up visits.

Health information will be collected from participants who are a part of this research study. By signing the consent form, participants will allow the primary investigator and researchers to use health information, but only to use it within this research. Information will only be used as explained in the consent form or when required by law.

Patient participation will require 7 visits as per routine care: 1 screening visit (15 minutes to determine if patient is qualified for study), 1 pre-operative visit (1-2 hrs to gather preliminary information), and 5 follow up visits at 6 weeks, 3 months, 6 months, 12 months, and 24 months (each requiring about 1 hour per visit).

The patients will be made known that participation in the study will not affect the standard of care delivered by the investigators. The risks of general anesthesia will be explained during the anesthesia consenting process as per standard of care. The use of BMP during lumbar fusion is currently approved by the FDA. Autograft, Allograft and BMAC have been used at NYULMC in the field of orthopaedics for inducing bone growth for non-unions and osteonecrosis of the extremities and has been used for the spine.

### **Document of Consent, Consent Forms**

Documentation of ICF process will be completed by IRB approved research staff. Subjects will be provided a copy of the signed ICF. The original ICF with study documentation will be physically stored in a secured location at the NYU HJD Spine Research Center. Participation is entirely voluntary. Participants can withdraw at any time without consequences of any kind. Participation or withdrawal from the study will not affect the patient's treatment in any way.

### **Potential Benefits**

The potential benefits to the subjects in this study are hypothesized to be similar in the 3 groups such as decreased and health-related quality of life measures previously defined, and presence of adequate fusion of spine. Additionally, there may be benefits of not having the high cost or complications associated with the usage of BMP. There may also not be any benefits present at all to the patient. However, from the patient's participation in the study, there will be a better understanding of the efficacy of allograft and BMAC use during lumbar spinal fusions with interbody support.

### **Adverse Events/Risks**

Although BMP is a frequently performed surgical procedure with easy use, complications with BMP, as with all surgeries with and without BMP of this type, are common and well documented in literature including, but not limited to, tumorigenesis, infections, seroma formation, or osteolysis. As the use of BMP to augment spinal instrumentation and fusion is a standard procedure, adverse events will be managed using standard surgical protocols.

PI: [name]

The use of allograft as a graft extender has become an acceptable practice especially in fusions employing interbody. The advantages of using of allograft rather than BMP during spinal fusion include decreased cost, similar structural support, and lack of BMP associated complications.

. In general, the use of autograft versus allograft should be balanced with donor site morbidity (pain, bleeding, infection) on the one hand, and the risk of pseudoarthrosis as well as the possibility of revision surgery on the other.

The disadvantages for allograft utilization include a higher potential for transmission of disease or infection, unavailability in some countries, immunogenicity with an inflammatory response, slower incorporation, and possible graft collapse. Allograft cancellous bone invokes a larger inflammatory response when compared to cortical allograft bone due to the larger surface area available for an immune response. In addition, cortical allografts are incorporated more slowly and to a lesser degree prior to remodeling than other allograft bone. In general, allograft is incorporated slower and less completely with decreased vascularization and osteoconduction than its autograft counterpart.

The safety of autologous bone marrow transplantation is quite good. Many surgeons now use bone marrow because of its biological value and low risk. One of the authors in the study by Hernigou et al. (P. Hernigou) has clinical experience with aspiration of bone marrow in more than 1000 patients, in which no complications were encountered. In this study, bone marrow aspirate will be collected in a minimally-invasive manner.

